However it is well known that spirometry is not routinely used in the ambulatory primary care setting¹¹⁻¹⁹ and minorities and the underserved population are less likely to have spirometry leading to greater prevalence of DE.²⁰⁻²⁵ It has been estimated that 30-50% of people with an existing diagnosis of asthma and COPD were found to be misdiagnosed.^{11,20,21,26-32} Many of these patients misdiagnosed with asthma and/or COPD receive unnecessary respiratory pharmacotherapy which can pose serious risks including pneumonia, cardiovascular events, and mortality.³³⁻⁵³ In the setting of DE, these are considered avoidable and unnecessary respiratory pharmacotherapy use in minorities and the underserved that are already disproportionately affected by cardiovascular disease⁵⁴⁻⁵⁶ increases the risk of poorer outcomes. There is also DE in the diagnosis of asthma versus COPD, as these are both clinically distinct respiratory disorders with nuances in treatment recommendations. It is reported that African-Americans are considered to have increasing COPD mortality and are disproportionately affected by asthma death rates.⁵⁷⁻⁶⁰ However, as spirometry is not routinely performed and DE is prevalent in asthma and COPD, a component of these poor outcomes may be attributable to missed or delayed diagnoses of other chronic conditions or misdiagnosis within asthma and COPD.

Barriers to the use of spirometry in primary care exist at provider and health systems levels. Previous studies show that primary care providers (PCPs) lack knowledge in existing guidelines and in implementing spirometry into primary care clinics.^{11,18,61-64} Beyond these barriers, PCPs struggle with logistical challenges such as time and workflow constraints with clinic visits lasting 15 minutes or less in patients with multiple chronic medical conditions.^{62,65} These predisposing and enabling factors explain why prior studies that included interventions to educate PCPs and incorporate spirometry by training personnel in primary care clinics have had limited results.^{32,63,66-68}

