2. If the spirometry findings are normal, with approval from the PCP, will de-escalate respiratory medication therapy via a stepwise process and schedule patient back for a repeat pre and post bronchodilator spirometry within 1-2 weeks at the same time and place as the PCP clinic session or the CRC (Clinical Research Center at UIC). Again with the PCP approval, this

deescalation and repeat spirometry can occur in 1-2 week intervals until all maintenance medications are discontinued as long as the pre and post spirometry continues to be normal. After each visit, the following will be provided to the provider and patient: a letter summarizing the interpretation of the findings using GOLD/GINA criteria with recommendations for initial guideline driven therapy based on GOLD/GINA guidelines, if appropriate. Subjects will be managed by their PCP thereafter.

3. All spirometry test results and the subject's assessment at the time of the test will be uploaded into the subject's electronic health record for future reference.

C) Patient subject- Usual Care:

On the day of the outpatient visit, subjects will be advised to arrive 60 minutes prior to their clinic visit in the same building as the clinic site or the CRC (Clinical Research Center). The following will be performed.

1. Subject demographic and contact information
2. Co-morbid conditions
3. Smoking history
4. Medication history from patient and also from pharmacy used by subjects
5. A respiratory exacerbation history in the past year
6. Modified Medical Research Counsel (mMRC) dyspnea scale and COPD assessment test
7. Quality of life measures

Subjects will be advised to go to their clinics and be managed by their PCP thereafter.

At the end of the 1 year followup, the patient will be scheduled for a pre and post BD spirometry and undergo the same spirometry protocol (de-escalation protocol) as the intervention group.

Based on spirometry findings:

1. If the spirometry findings are consistent with COPD and/or asthma, the following will be provided to the provider and patient: a letter summarizing the interpretation of the findings using GOLD/GINA criteria with recommendations for initial guideline driven therapy based on GOLD/GINA guidelines. Subjects will be managed by their PCP thereafter.

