2. If the spirometry findings are normal, with approval from the PCP, will de-escalate respiratory medication therapy via a stepwise process and schedule patient back for a repeat pre and post bronchodilator spirometry within 1-2 weeks at the same time and place as the PCP clinic session. Again with the PCP approval, this deescalation and repeat spirometry can occur in 1-2 week intervals until all maintenance medications are discontinued as long as the pre and post spirometry continues to be normal. After each visit, the following will be provided to the provider and patient: a letter summarizing the interpretation of the findings using GOLD/GINA criteria with recommendations for initial guideline driven therapy based on GOLD/GINA guidelines, if appropriate. Subjects will be managed by their PCP thereafter.
3. All spirometry test results and the subject's assessment at the time of the test will be uploaded into the subject's electronic health record for future reference.

D) Outcome Measures:

1. Primary outcome:

- (i) Accurate classification of patient as having COPD and/or asthma
- (ii) All-cause and respiratory related, acute care outpatient visits, ED visits, and hospitalizations

2. Secondary outcome:

- (i) Appropriate use of respiratory medications based on guidelines
- (ii) Use of other diagnostic testing: ECG, echocardiograms, CT/CXR, stress testing, cardiac catheterization, other pulmonary function tests
- (iii) Initiation of guideline based therapy
- (iv) Quality of life measures

E) Data collection and follow-up

1) Baseline data collection obtained at visit zero (V_0), in addition to those listed under intervention and usual care:

- 1. Demographic data (gender, age, self-reported race)
- 2. SES related measures: median household income
- 3. Level of education
- 4. Type of health insurance or self-pay
- 5. Up to two emergency contacts information
- 6. List of current respiratory medications from subject's pharmacy and verification with patient
- 7. Co-morbidities
- 8. History of prior ED visits or hospitalizations in the past one year with associated cause
- 9. EQ-5D 5L +B Bolt-on
- 10. SF-36 short form
- 11. Social support survey

2) All subjects will have their medical charts reviewed every 3 months after the initial visit (MR_1 , MR_2 , MR_3 , MR_4) up to one year. These electronic medical chart reviews will be used to obtain follow-up data since last study contact.

- 1. Change in type of health insurance or self-pay

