- 2. List of current respiratory medications from subject's pharmacy and verification with patient
- 3. Use of diagnostic testing: ECG, echocardiograms, CT/CXR, stress testing, cardiac catheterization, other pulmonary function tests
- 4. Any ED visits or hospitalizations or acute outpatient care visit and associated cause.
- 5. Healthcare utilization outside of U of I system (e.g. testing such as spirometry, ED and hospitalizations) if available through scanned records

3) All subjects will be contacted every 3 months after the initial visit via telephone (T_1 , T_2 , T_3 , T_4) up to one year; or they will be given the option to complete in person based on subject's convenience, for example they have a doctor appointment near time of study follow-up. These phone calls will be used to obtain follow-up data since last study contact. A reminder post-card will be mailed to the subjects a month before the next telephone contact.

- 1. Change in type of health insurance or self-pay

2. List of current respiratory medications from subject's pharmacy and verification with patient
3. Use of diagnostic testing: ECG, echocardiograms, CT/CXR, stress testing, cardiac catheterization, other pulmonary function tests
4. Any ED visits or hospitalizations or acute outpatient care visit and associated cause.
5. Healthcare utilization outside of U of I system (e.g. testing such as ancillary testing, ED and hospitalizations)
6. mMRC
7. A respiratory exacerbation history
8. EQ-5D 5L +B Bolt-on
9. SF-36 short form (at 3, 6 and 12 months)
10. Social support survey (at 6 months and 12 months)

F) Monetary compensation of subjects

1. PCP compensation:

UI Health and MSHC PCPs will receive \$95 in cash after completion of the education session. For CCHHS PCPs, the Division or Department will receive a total of \$95 per participant to be part of the divisional fund to be used by the PCP at their discretion as allowed by their institution.

2. Patient subject compensation:

Baseline visit (Vo):

Same for Intervention and usual care groups: Subjects will be provided \$75 in cash for completing the initial study visit.

Telephone contact (T₁-T₃):

Same for Intervention and usual care groups. Subjects who choose to complete the follow-up in person or via telephone will receive \$20 in cash at the time of the visit or at a later specified time that is convenient for the subject.

Final contact (T₄):

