For **Aim 3: Costs**: The intervention costs for the study include the cost of the spirometry test, the time of the CHW/health promoter, and time of pulmonologist to provide periodic oversight of spirometry validity. In addition to estimating the costs associated with the intervention it will be important to measure the healthcare utilization for participants included in the study. It is possible that the intervention leads to use of other healthcare resources, particularly if the patient is determined to be free of respiratory disease. Therefore, we will measure both respiratory-related and overall healthcare costs. To measure these costs, we will determine overall healthcare utilization and apply unit costs to each of the events. Using chart reviews, we will examine healthcare utilization during the follow-up period. We will categorize healthcare utilization into either respiratory-related or all other healthcare use. We will apply standardized prices to each of the utilization components to estimate the overall and respiratory-related healthcare resource use during the study period. The standardize prices will be based on either the National Committee for Quality Assurance standardize price list for their relative resource use measure or Medicare reimbursement rates. For medications, we will rely on average wholesale price of medications to assign an average price to each of the COPD and asthma-related medications.

Cost-Effectiveness: The secondary outcome measures included in the study will be used to estimate the effectiveness to be used in the cost-utility analysis. We will use responses to the EQ5D to estimate patient utility and use that in calculation of quality-adjusted life-years (QALY). The area under the curve will be compared between the two groups and the difference will be the incremental effect used in the cost-utility analysis.

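### Respiratory-related events are attributed without a stated rule, from sources that hold study spirometry in one arm only during follow-up, so attribution can differ by arm

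*Combined protocol and SAP*

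**What the plan says.** Primary outcome (ii) in section 4.D is "All-cause and respiratory related, acute care outpatient visits, ED visits, and hospitalizations". The three-monthly chart reviews and the three-monthly patient contacts in section 4.E both record "Any ED visits or hospitalizations or acute outpatient care visit and associated cause". Neither place says what makes a cause respiratory. Section 7 (Storage of Data) says that staff of each institution review that institution's records; it mentions no masking or adjudication.

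In the intervention arm (section 4.B), "All spirometry test results and the subject's assessment at the time of the test will be uploaded into the subject's electronic health record". After a normal result, "the following will be provided to the provider and patient: a letter summarizing the interpretation of the findings using GOLD/GINA criteria"; a similar letter follows a result consistent with COPD or asthma. For usual care (section 4.C), "At the end of the 1 year followup, the patient will be scheduled for a pre and post BD spirometry", with the upload and letters following then.

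For Aim 3 (section 5), the plan states: "We will categorize healthcare utilization into either respiratory-related or all other healthcare use". No rule or code list is given. The ICER numerator combines intervention cost with respiratory-related use. A version using overall utilization is planned as a sensitivity analysis, and the plan gives imperfect identification of respiratory costs as one of its reasons.

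**The concern.** Every patient enters with an asthma or COPD diagnosis. During the outcome year, only the intervention arm has a study result and assessment that may lead a treating clinician, a patient or a chart reviewer to see a later breathlessness visit differently. The same visit could then be counted as respiratory in usual care and as something else in the intervention arm.

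That would be outcome misclassification that depends on arm. It would affect part of a primary outcome and the event-cost part of the ICER numerator. Aim 2 hypothesises lower utilization, and a visit filed under another cause is still a visit. A lower respiratory count produced this way would not be evidence for that hypothesis.

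**Working it through.** The documents give no event rate, intracluster correlation (ICC), effect size or power calculation for this outcome, so there is no planned figure to reproduce. The argument rests on the text; the arithmetic only shows what size the artefact could have.

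**Sources of attribution during follow-up**

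- Study spirometry and assessment in the record: intervention from near baseline; usual care after the one-year follow-up.
- Interpretation letter to provider and patient: same timing.
- Cause of each event: same two sources in both arms (chart and patient contact). In the intervention arm both can be influenced by the result.

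**Illustration with no true change in events**

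- m = share of respiratory-labelled events that occur in patients who would lose the label. Background and Significance reports that "30-50% of people with an existing diagnosis of asthma and COPD were found to be misdiagnosed". Using m = 0.30 to 0.50 assumes that all misdiagnosed patients qualify and that events are spread evenly over patients. This is an upper range: some misdiagnosis is confusion between asthma and COPD, where events stay respiratory.
- r = share of those events relabelled in the intervention arm. The documents give no value; 25% and 50% are assumed.
- Spurious rate ratio = 1 − m × r.

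| r | m = 0.30 | m = 0.50 |
|---|---|---|
| 25% | 1 − 0.075 = 0.925 | 1 − 0.125 = 0.875 |
| 50% | 1 − 0.15 = 0.85 | 1 − 0.25 = 0.75 |

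The all-cause rate ratio stays at 1.00 throughout. If relabelled events have average cost, respiratory event cost falls by the same 7.5% to 25% while total event cost is unchanged. Intervention cost and the EQ-5D-based QALY difference are not affected.

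**What this could do to the test**

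Further assumptions: 250 patients per arm (the plan's 250/250 split is by site, not arm), 0.5 respiratory events per patient-year in usual care, overdispersion 1.5, and ICC 0.01 to 0.05.

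- Patients per provider: 500 / 80 = 6.25, using the maximum number of providers.
- Design effect: 1 + 5.25 × ICC = 1.05 to 1.26.
- Variance of the log rate ratio: 1.5 × design effect × (1/E0 + 1/E1), with E0 = 250 × 0.5 = 125 and E1 = 125 × rate ratio.
- At r = 50%, the chance of a two-sided p < 0.05 in favour of the intervention is about 14-16% for m = 0.30 and 33-39% for m = 0.50. The nominal figure in that direction is 2.5%.

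These probabilities move widely with the assumed event rate and should be read as orders of size only.

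**The case against.** The strongest reply is that the plan already has measures that relabelling cannot touch. All-cause use stands beside respiratory use in primary outcome (ii), and Aim 2 names all-cause emergency visits and hospitalizations. For costs, the authors foresaw imprecise attribution and planned the overall-cost analysis. A pure labelling artefact would show as a respiratory benefit with no all-cause benefit. This stands, and it limits the harm. It leaves open which result governs if they disagree, and the main ICER remains respiratory-only.

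A reader might infer that the intervention strips the diagnosis from the record and so builds in a bias in its own favour. The documents do not support that. They provide for an upload and a letter, not for removal of a diagnosis, and whether later visits would be recorded differently is an inference. The direction is not fixed either: confirmed disease, or visits after medication de-escalation, could raise respiratory labelling in the intervention arm. Usual-care providers attend the same education session and are not barred from ordering spirometry themselves, which could narrow the contrast.

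A reader might also infer that chart reviewers know the arm. The plan is silent on this. Masking them would not settle the matter in any case, because clinicians write the cause before the reviewer sees it.

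**Conclusion.** The concern holds as a risk. As written, the plan lets attribution of respiratory-related events differ by arm, and it has no rule to limit this. It is worth correcting in the analysis plan because a primary outcome component and the main ICER are exposed and the correction is cheap.

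The illustrated size, a spurious rate ratio of 0.75 to 0.93, depends on an assumed relabelling share of 25-50%, an even spread of events, and the upper-range reading of the misdiagnosis figure. The true size may be smaller, and the sign could be reversed. The documents do not support saying that the respiratory result will be biased towards the intervention, or that the trial's utilization conclusion as a whole is compromised.

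**What to change.** 1. Before any analysis by arm, define respiratory-related by one fixed list, applied by program without the arm variable. Apply it to the presenting reason or chief complaint as well as to the diagnosis code, and count the event if either field matches. The list would hold the asthma and COPD codes already given in section 3, plus dyspnea, wheeze, cough and lower respiratory infection. Map patient-reported reasons to the same list, and use the same classification for the Aim 3 costs.
2. State that a respiratory-related benefit will be read together with the all-cause result, and will not be claimed as reduced utilization if all-cause use shows no reduction. Report the overall-cost ICER with the same prominence as the respiratory-only ICER. Both analyses are already planned.

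The cost is analysis-plan wording and programming, with no extra reader. If the chart form does not already capture the presenting reason, it needs that field. Some non-respiratory breathlessness will be counted in both arms, which dilutes the outcome slightly. The list reduces label-driven differences but does not remove them: a visit for which both fields name an unlisted cause, such as heart failure or anxiety, can still drop out in one arm. That is why the second step is needed alongside the first.

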5. STATISTICAL ANALYSES

All data will be stored in a secure, locked location. Data will be entered and managed through the Research Electronic Data Capture (REDCap). REDCap is a secure web-based application for building and managing online databases. REDCap is provided by

the CCTS Design Analysis Core. Data will be analyzed for clinical effectiveness using intention-to-treat principles.⁶⁹⁻⁷¹ For **Aim 1**, we will evaluate the misdiagnosis rates of the intervened and usual care groups separately at the first visit. Then compare rates between groups by using a generalized linear mixed model for binary outcome with two cluster levels, PCP and hospital, to account for the dependence within clusters. For the **Aim 2**, to investigate the impact of the misdiagnosis over time (4 time points: 0, 3, 6, 9, 12 months) on the quality of life and healthcare utilization, we will fit generalized linear mixed models with time, group, and their interaction as the main predictors. Two cluster levels, PCP and hospital, will be specified in the model to account for the dependence within clusters^{72,73} and an appropriate link function will be used for each outcome. Clinical important confounders will also be adjusted in the models. Before these analyses we will use descriptive statistics to describe the sample, and any assumption behind each statistical method will be examined during the analysis. A two-sided p-value less than 0.05 would be considered as statistical significance. All the analyses will be conducted by using SAS 9.2 (SAS Inst., Cary, NC).

For **Aim 3: Costs**: The intervention costs for the study include the cost of the spirometry test, the time of the CHW/health promoter, and time of pulmonologist to provide periodic oversight of spirometry validity. In addition to estimating the costs associated with the intervention it will be important to measure the healthcare utilization for participants included in the study. It is possible that the intervention leads to use of other healthcare resources, particularly if the patient is determined to be free of respiratory disease. Therefore, we will measure both respiratory-related and overall healthcare costs. To measure these costs, we will determine overall healthcare utilization and apply unit costs to each of the events. Using chart reviews, we will examine healthcare utilization during the follow-up period. We will categorize healthcare utilization into either respiratory-related or all other healthcare use. We will apply standardized prices to each of the utilization components to estimate the overall and respiratory-related healthcare resource use during the study period. The standardize prices will be based on either the National Committee for Quality Assurance standardize price list for their relative resource use measure or Medicare reimbursement rates. For medications, we will rely on average wholesale price of medications to assign an average price to each of the COPD and asthma-related medications.

Cost-Effectiveness: The secondary outcome measures included in the study will be used to estimate the effectiveness to be used in the cost-utility analysis. We will use responses to the EQ5D to estimate patient utility and use that in calculation of quality-adjusted life-years (QALY). The area under the curve will be compared between the two groups and the difference will be the incremental effect used in the cost-utility analysis.

Cost-utility analyses: We will evaluate the cost-utility of the intervention compared to usual care over the study period using recommended methods for cost-effectiveness analysis.⁷⁴ To compare the cost-effectiveness of the intervention to usual care, the findings are summarized into a ratio that provides the results in terms of the costs per unit of effect. We will calculate the difference in intervention costs and respiratory-related healthcare resource use between groups to determine the numerator of the ratio and the denominator will be the difference in QALYs in the cost-utility analysis. These incremental cost-effectiveness ratios (ICERs) will represent the cost per gain in QALYs for the intervention compared to standard care. As part of the cost-utility analysis we will evaluate the uncertainty associated with the ICERs. We will use bootstrapping

methods to generate confidence limits for the ICERs.^{75,76} We will display the results graphically on a cost-effectiveness plane and generate cost-effectiveness acceptability curves for the intervention compared to usual care.^{77,78} Cost-effectiveness acceptability curves display the probability of the intervention being cost-effective given various threshold values.⁷⁸ Thus decision-makers can identify a threshold value appropriate for their setting and determine the probability that the intervention will be cost-effective. We will also conduct sensitivity analyses that use the measure of overall healthcare utilization in calculation of the costs, as there may not be perfect specificity in identifying respiratory-related costs during the follow-up assessments and the intervention may lead to differences in non-respiratory costs.

